- BVY (25 participants): 16.0% (4 participants)

The higher frequency of treatment-related AEs in the SC GS-6207 total group was mainly because of ISRs, as reflected in the most common AEs considered related to study drugs:

- GS-6207 total group (157 participants), excluding ISRs: nausea (5.1%, 8 participants), diarrhea and headache (each 2.5%, 4 participants), and fatigue (1.9%, 3 participants)
- SC GS-6207 total group (105 participants), only ISRs: injection site erythema (26.7%, 28 participants), injection site swelling (22.9%, 24 participants), injection site pain (19.0%, 20 participants)
- Oral GS-6207 + DVY (52 participants): nausea and diarrhea (each 3.8%, 2 participants), fatigue, headache, dyspepsia, flatulence, vomiting, weight increased, influenza, overdose, and hot flush (each 1.9%, 1 participant)

- BVY (25 participants): dyspepsia, salivary hypersecretion, insomnia, and weight increased (4.0%, 1 participant)

Overall, 57 of 103 participants (55.3%) who received SC GS-6207 had a study drug-related ISR; all were Grade 1 or Grade 2, except for 1 participant with a Grade 3 injection site nodule. There were no new Grade 3 or higher ISRs reported since the Week 28 analysis. The most frequently reported ISRs ($\geq 10\%$ in SC GS-6207 total group) and their duration in median (Q1, Q3) days were as follows:

- Injection site erythema (27.2%, 28 participants), 5 (2, 11) days
- Injection site swelling (23.3%, 24 participants), 11 (6, 29) days
- Injection site pain (19.4%, 20 participants), 4 (1, 9) days
- Injection site nodule (14.6%, 15 participants), 195 (122, 301) days
- Injection site inflammation (13.6%, 14 participants), 3 (1, 8) days
- Injection site induration (12.6%, 13 participants), 202 (101, 361) days

Overall, 15 of 103 participants had an AE of injection site nodule and 13 of 103 participants had an AE of injection site induration. All were Grade 1 or Grade 2, except for 1 participant with a Grade 3 injection site nodule. Ongoing and resolved injection site indurations and nodules were as follows:

ISRs after the first SC GS-6207 injection at Day 15:

Participant-level analysis:

- Nodules: Ongoing (1 of 11 [9.1%]); Resolved (10 of 11 [90.9%])
- Indurations: Ongoing (6 of 9 [66.7%]); Resolved (3 of 9 [33.3%])

Event-level analysis:

- Nodules: Ongoing (1 of 13 [7.7%]); Resolved (12 of 13 [92.3%])
- Indurations: Ongoing (6 of 9 [66.7%]); Resolved (3 of 9 [33.3%])

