1.2. Study Design

Design Configuration and Subject Population

This is a Phase 2, randomized, open label, active controlled, multicenter study.

Approximately 175 treatment-naive PWH who meet all eligibility criteria will be randomized in a 2:2:2:1 ratio to 1 of the following 4 treatment groups. Randomization will be stratified by HIV-1 RNA level ($\leq 100,000$ copies/mL or $> 100,000$ copies/mL) at screening.

Treatment Groups

Treatment Group 1 (n = 50)

Induction: Subjects will receive oral LEN 600 mg, 600 mg, and 300 mg, without regard to food, at Days 1, 2, and 8 respectively. Subjects will also begin oral daily emtricitabine (F)/TAF (200/25 mg), without regard to food from Day 1 onwards for a total of 28 weeks. On Day 15 subjects will receive subcutaneous (SC) LEN 927 mg, without regard to food.

Maintenance: Subjects will receive SC LEN 927 mg at Week 28 and every 26 weeks thereafter. Subjects will discontinue oral daily F/TAF (200/25 mg) at Week 28 and begin taking oral daily TAF (25 mg), without regard to food.

Treatment Group 2 (n = 50)

Induction: Subjects will receive oral LEN 600 mg, 600 mg, and 300 mg, without regard to food at Days 1, 2, and 8 respectively. Subjects will also begin oral daily F/TAF (200/25 mg), without regard to food from Day 1 onward for a total of 28 weeks. On Day 15 subjects will receive SC LEN 927 mg, without regard to food.

Maintenance: Subjects will receive SC LEN 927 mg at Week 28 and every 26 weeks thereafter. Subjects will discontinue oral daily F/TAF (200/25 mg) at Week 28 and begin oral daily BIC (75 mg) without regard to food.

Treatment Group 3 (n = 50)

Subjects will receive oral LEN 600 mg and 600 mg without regard to food at Days 1 and 2, respectively. On Day 3, subjects will begin oral daily LEN 50 mg, without regards to food. Subjects will begin oral daily F/TAF (200/25 mg), without regard to food from Day 1 onwards.

Treatment Group 4 (n = 25)

Subjects will receive oral daily bictegravir/emtricitabine/TAF (B/F/TAF, 50/200/25 mg), without regard to food at Day 1 and throughout their participation in the study.

Key Eligibility Criteria

Treatment naive PWH who meet the following criteria:

- Age \geq 18 years of age at Screening
- Plasma HIV-1 RNA \geq 200 copies/mL at Screening
- CD4+ cell count \geq 200 cells/ μ L at Screening

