3.8. Analysis Visit Windows

3.8.1. Definition of Key Dates and Study Day

Study Day 1 is defined as the day when the first dose of study drug was taken, as recorded on the Study Drug Administration eCRF. For subjects in Treatment Groups 1-3, the earliest of the first dose dates of any component (ie, LEN or F/TAF) is considered as the first dose date of the study drug.

Last Dose Date is defined as follows for subjects who prematurely discontinued study drug according to Study Drug Completion eCRF.

- For subjects who receive SC injection, the last dose date is defined as the latest nonmissing end date of the study drug used with LEN.
- For subjects who do not receive SC injection, the last dose date is defined as the earliest of the last dose date of any study drug.
- If the date of last dose is incomplete or missing (eg, due to lost to follow-up), the latest nonmissing study drug start dates and end dates, the clinic visit dates, and the laboratory visit dates excluding the dates of any follow-up visits will be used to impute the last dose date.

Study Days are calculated relative to Study Day 1 of study drug and derived as follows:

- For postdose study days: Assessment Date – First Dose Date + 1
- For days prior to the first dose: Assessment Date – First Dose Date

Baseline Value is defined as the last value obtained on or prior to the first dose of study drug.

Last Study Date is the latest nonmissing clinic visit dates, and/or the laboratory visit dates, and/or latest AE onset date and end date, whichever is latest, including the any follow-up visit dates, for subjects who prematurely discontinued study according to the Study Completion eCRF.

Last Exposure Date is defined as follows for subjects who prematurely discontinued study drug according to Study Drug Completion eCRF. This date is defined considering the prolonged exposure of LEN after the last dose date of LEN.

- Treatment Groups 1 and 2:
 - For subjects who receive SC injection, last exposure date is defined as last study date.
 - For subjects who do not receive SC injection, last exposure date is defined as the minimum of the last dose date plus 60 days and the last study date.

- Treatment Group 3: last exposure date is defined as the minimum of the last dose date plus 60 days and the last study date.
- Treatment Group 4: last exposure date is defined as the minimum of the last dose date plus 30 days and the last study date.

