7.1.5.2. Incomplete Dates

If the onset date of the AE is incomplete and the AE stop date is not prior to the first dose date of study drug, then the month and year (or year alone if month is not recorded) of onset determine whether an AE is treatment emergent. The event is considered treatment emergent as follows:

- Subjects who receive SC injection: the AE onset date is the same as or after the month and year (or year) of the first dose date of study drug
- Subjects who do not receive SC injection:
 - The AE onset is the same as or after the month and year (or year) of the first dose date of study drug, and
 - The AE onset date is the same as or before the month and year (or year) of the last exposure date

An AE with completely missing onset and stop dates, or with the onset date missing and a stop date later than the first dose date of study drug, will be considered to be treatment emergent. In addition, an AE with the onset date missing and incomplete stop date with the same or later month and year (or year alone if month is not recorded) as the first dose date of study drug will be considered treatment emergent.

When calculating the duration of event or time to onset, the following imputation rule will be used:

Missing start month/day: Jan 1/first day of the month will be used unless this is before the start date of study drug; in this case the study drug start date will be used;

Missing stop month/day: Dec 31/last day of the month will be used, unless this is after the last study date; in this case the last study date will be used.

Completely missing start or end dates will remain missing, with no imputation applied.

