7.1.7. Additional Analysis of Adverse Events

7.1.7.1. Study Drug Related Injection Site Reactions

Additional analysis of AEs will be performed for injection site reaction (ISR) related to study drug, which is defined as an AE related to study drug reported as any event within the MedDRA HLT of “Injection Site Reactions”. The following summaries will be provided for each SC injection visit (eg, Day 1, Week 28) and the overall for subjects in Treatment Groups 1 and 2.

- Number of subjects that received SC injection(s)
- Number and percentage of subjects with study drug related ISRs
- Number and percentage of subjects with study drug related ISRs by grade
- Number and percentage of subjects with study drug related ISRs by PT

The denominator for the percentage calculation for the by visit summary and the overall summary will be based on the total number of subjects who receive at least 1 SC injection at the visit of interest and the total number of subjects who receive at least 1 SC injection at any injection visit, respectively.

Duration of the ISR will also be calculated and summarized. Duration of a given ISR event is defined as the ISR stop date minus the ISR onset date plus 1 day. For ISRs with ongoing stop date, stop date will be imputed as last study date or data cut date, whichever is the earliest. Duration of ISR events in days will be summarized using descriptive statistics.

A by-subject listing for study drug-related ISRs and the corresponding duration will be provided.

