- a) To summarize ISRs by injection visit, each study drug related ISR will be associated with one injection visit (eg, Day 15 SC injection, Week 28 SC Injection, Week 54 SC injection) based on the start date of the ISR. If the start date of the ISR is on or after a given injection visit date and prior to the next injection visit date, if available, the ISR will be associated with that injection visit.
- b) For ISR summarized by PT:
 - i) For the overall summary (ie, subjects received at least one injection), multiple ISRs with the same PT will only be counted once per subject for each PT.
 - ii) For by visit summary (ie, subjects received injection for a given injection visit), multiple ISRs associated with the injection visit of interest with the same PT will only be counted once per subject for each PT.
- c) For ISR summarized by grade:
 - i) For the overall summary (ie, subjects received at least one injection), the most severe grade based on all ISRs will be used.
 - ii) For by visit summary (subjects received injection for a given injection visit), the most severe grade from all ISRs associated with the injection visit of interest will be used.

16) Concomitant nonstudy-drug ARV medications (ie, ARV medications other than study drug that are taken on or after first dose date) will be flagged in “Antiviral Medication” listings.

17) Graded Laboratory Abnormalities Summary

18) The following labels will be used for treatment-emergent laboratory abnormalities and treatment-emergent Grade 3 or 4 laboratory abnormalities summary tables and listings:

Battery	Lab Test Label Used in I-labtox Listing	Toxicity Direction	Lab Test Label Used in t-labtox Table
Hematology	Hemoglobin (Hb)	Decrease	Hemoglobin (Decreased)
	Neutrophils	Decrease	Neutrophils (Decreased)
	Platelets	Decrease	Platelets (Decreased)
	WBC	Decrease	WBC (Decreased)
Chemistry	Albumin	Decrease	Albumin (Decreased)
	Alkaline Phosphatase	Increase	Alkaline Phosphatase (Increased)
	ALT	Increase	ALT (Increased)
	Amylase	Increase	Amylase (Increased)
	AST	Increase	AST (Increased)
	Bicarbonate	Decrease	Bicarbonate (Decreased)
	Corrected Calcium	Increase	Corrected Calcium (Hypercalcemia)
	Corrected Calcium	Decrease	Corrected Calcium (Hypocalcemia)
	Creatine Kinase (CK)	Increase	Creatine Kinase (Increased)
	Creatinine	Increase	Creatinine (Increased)
	GGT	Increase	GGT (Increased)
	Lipase	Increase	Lipase (Increased)
	Magnesium	Decrease	Magnesium (Hypomagnesemia)

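### For an injection site reaction with a missing onset day, the SAP's imputed onset can precede the injection and overstate duration, and the date used for linkage to an injection is not stated.

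*SAP*

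**What the plan says.** SAP 7.1.5.2 gives the imputation rule and its scope: "When calculating the duration of event or time to onset, the following imputation rule will be used". The rule for onset is: "Missing start month/day: Jan 1/first day of the month will be used unless this is before the start date of study drug"; in that case the study drug start date is used instead. No other floor is given.

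Study drug start comes before any injection. SAP 3.8.1: "Study Day 1 is defined as the day when the first dose of study drug was taken". For Treatment Groups 1 and 2 that is an oral dose. The first injection comes two weeks later (SAP 1.2): "On Day 15 subjects will receive subcutaneous (SC) LEN 927 mg, without regard to food". The next is at Week 28, then every 26 weeks.

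Two ISR outputs use the onset date:

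- **Duration** (SAP 7.1.7.1): "Duration of a given ISR event is defined as the ISR stop date minus the ISR onset date plus 1 day".
- **By-injection tables** (SAP 7.1.7.1): "The following summaries will be provided for each SC injection visit (eg, Day 1, Week 28) and the overall". The Day 1 example there disagrees with SAP 1.2, 7.1.7.2 and Appendix 3, which all put the first injection at Day 15. Section 7.1.7.2 adds ongoing and resolved counts per injection for nodules and induration.

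Appendix 3 item 15(a) makes the link to an injection. The ISR belongs to a visit "If the start date of the ISR is on or after a given injection visit date and prior to the next injection visit date". It does not mention partial dates.

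**The concern.** A drug-related reaction at an injection site cannot start before the injection. The imputation rule allows it, because its only floor is the first oral dose. Following the rule as written counts days before the injection in the duration of the reaction.

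The acute reactions are short. Protocol 1.2.2.8 reports "Injection site erythema (27.2%, 28 participants), 5 (2, 11) days" (median, with quartiles), and medians of 11 days for swelling, 4 for pain and 3 for inflammation. An error of one to two weeks on such an event is several times its true length.

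The by-injection tables raise a second question. If a programmer carried the imputed date into item 15(a), some ISRs would move to an earlier injection or match none. Those tables have small counts. Protocol 1.2.2.8 reports induration ongoing in 3 of 6 participants after the Week 28 injection; taking one ongoing participant out gives 2 of 5, so 50% becomes 40%.

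**Working it through.** The documents give no figure for this error, so there is none to reproduce.

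**Inputs.** The imputation rule and its floor (SAP 7.1.5.2); Day 1 as study drug start (3.8.1); first injection on Day 15, 14 days later, and the next at Week 28, nominal study day 196 (1.2 and Table 3-1); duration as stop minus onset plus 1 (7.1.7.1). Assumptions: injection dates are spread evenly over the calendar, the day is missing but month and year are known, and the lag from injection to onset is as stated below.

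**Step 1: illustration.** Take an injection on the 20th and a reaction starting that day and ending on the 24th. True duration is 24 − 20 + 1 = 5 days.

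- Week 28 injection: imputed onset is the 1st, so duration is 24 − 1 + 1 = 24 days, 19 too many.
- Day 15 injection: Day 1 was the 6th, so the floor applies and duration is 24 − 6 + 1 = 19 days, 14 too many.

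**Step 2: how often the imputed onset precedes the injection.** If onset falls in the injection's month, the imputed date precedes the injection unless the injection was on the 1st. If onset falls in a later month, it does not. For lag L, a month of n days has n − L − 1 injection dates that go wrong (not below zero). Over a 365-day year this sums to 353 − 12L for lags up to 27 days.

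| Assumed lag (days, uniform) | Share dated before the injection |
|---|---|
| 0 | 353/365 = 96.7% |
| 0–3 (mean 1.5) | 335/365 = 91.8% |
| 0–7 (mean 3.5) | 311/365 = 85.2% |
| 0–14 (mean 7) | 269/365 = 73.7% |
| 0–30 | 47.5% (by enumeration) |
| 0–60 | 24.2% (by enumeration) |

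The shares are the same for the Day 15 and Week 28 injections.

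**Step 3: duration error, Week 28 and later.** The first of the month is after Day 1, so the error is the true onset's day of month minus 1. Monthly sums are 465, 435 and 378 for months of 31, 30 and 28 days. The total is 7 × 465 + 4 × 435 + 378 = 5373, and 5373/365 = 14.7 days, with a maximum of 30. This does not depend on the lag.

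**Step 4: duration error, Day 15, same-day onset.** The error is the smaller of day of month minus 1 and 14. Monthly sums are 105 + 14 × (n − 15), that is 329, 315 and 287. The total is 7 × 329 + 4 × 315 + 287 = 3850, and 3850/365 = 10.5 days, with a maximum of 14. For lags of 0 to 7 days, enumeration gives a mean of 12.1 and a maximum of 21.

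**Step 5: scale.** For erythema, 14.7/5 is 2.9 times the reported median. For nodules, 14.7/195 = 7.5%; for induration, 14.7/202 = 7.3%.

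**Step 6: linkage, only if the imputed date were used.** An affected Day 15 ISR would fall before all injections and match none. An affected Week 28 ISR would fall at most 30 days before that injection, well after Day 15, and would be assigned to Day 15.

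**The case against.** A reader might infer that the SAP assigns these ISRs to the wrong injection. It does not say so. Section 7.1.5.2 limits the imputed date to duration and time to onset, and the same section decides treatment emergence from the recorded month and year. Item 15(a) never invokes the imputed date. What the documents show is a missing linkage rule. That gap is real, since SAP 3.6.1 sends incomplete onset dates to 7.1.5.2, which gives no other day-level date.

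A reader might also infer that the imputed onset almost always precedes the injection, or that every duration grows by two weeks. The first holds only for onset within a few days; late-onset nodules or induration would be affected less often. The second ignores the Day 1 floor. With the month missing too, the error does not generally approach a year either: for same-day onset the floor caps it at 14 days for Day 15 and 195 days for a nominal Week 28 visit.

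The effect may also be small in practice. Injections are given on site, participants receive an ISR worksheet, and data are queried for completeness. The reported upper quartiles (erythema 11 days, pain 9, inflammation 8) lie below the 14.7-day mean error, so partial dates are unlikely to be common. Earliest-date imputation also lengthens harm rather than hiding it.

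These points limit the size and rule out a claim of mislinkage. They do not make an onset before the injection correct.

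**Conclusion.** The point holds for duration. The stated rule can date a drug-related ISR before its injection and count those days. For an affected event, the mean overstatement is 14.7 days at Week 28 and later injections, and 10.5 days for same-day onset at Day 15. It matters for acute reactions and little for nodules and induration.

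For linkage, the conclusion is only that item 15(a) is silent on partial dates; misassignment would follow if the imputed date were carried over. Overall ISR incidence, preferred-term and grade summaries do not use linkage and are unaffected.

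The sizes rest on evenly spread injection dates and on assumed lags. The number of partial-date ISRs is not given, so the effect on the reported summaries cannot be sized and is probably small. This is a minor improvement.

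**What to change.** In SAP 7.1.5.2 and Appendix 3 item 15, add a rule for study-drug-related events in the Injection Site Reactions HLT with a partial onset date:

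- If onset month and year are known, and an SC injection was given in that month and is not after the event's stop date, floor the imputed onset at that injection date.
- In all cases, including a missing month, do not impute onset before the first SC injection.
- Do not default to the latest injection. With the month missing, that could move a Day 15 reaction to a later injection.
- Use the same date for duration and for linkage.

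With the day missing and the month known, this brings onsets before the causal injection to 0%. Mean overstatement falls to 0 days for same-day onset, 1.4 for lags of 0 to 3 days, 3.2 for 0 to 7 and 9.7 for 0 to 30.

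There is one small downside: a late reaction to an earlier injection that began earlier in the month of the next injection would be credited to the next one.

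The cost is a short SAP paragraph and a small derivation change. Protocol 1.2.2.8 already reports Week 54 results, so apply the rule from the Week 80 analysis onward, document it in the CSR as SAP Section 1 requires, and state how many ISRs had a partial onset date. Correct the Day 1 example in 7.1.7.1 at the same time.

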7.1.6. Summaries of Adverse Events and Deaths

TEAEs will be summarized based on the Safety Analysis Set.

7.1.6.1. Summaries of AE incidence in Combined Severity Grade Subsets

A brief, high-level summary of the number and percentage of subjects who experienced at least 1 TEAE in the categories described below will be provided by treatment group. All deaths observed in the study will also be included in this summary.

The number and percentage of subjects who experienced at least 1 TEAE will be provided and summarized by treatment group, SOC and PT, and by PT only for the following AE categories:

- TEAEs
- TEAEs (by severity)
- TEAEs with Grade 3 or higher (by severity)
- TEAEs with Grade 2 or higher
- TE treatment-related AEs
- TE treatment-related AEs with Grade 3 or higher (by severity)
- TE treatment-related AEs with Grade 2 or higher
- TE SAEs
- TE treatment-related SAEs
- TEAEs leading to premature discontinuation of study drug
- TEAEs leading to premature discontinuation of study
- TEAEs leading to death (by SOC and PT only)

Multiple events will be counted only once per subject in each summary. Adverse events will be summarized and listed first in alphabetic order of SOC, and then by PT in descending order of total frequency within each SOC. For summarizes by PT only, AEs will be summarized and listed by PT in descending order of total frequency.

In addition, data listings will be provided for the following:

- All AEs
- All SAEs
- All Deaths
- All AEs with severity of Grade 3 or higher
- All AEs leading to premature discontinuation of study drug
- All AEs leading to premature discontinuation of study

For each listing, whether the event is treatment emergent will be indicated.

7.1.7. Additional Analysis of Adverse Events

7.1.7.1. Study Drug Related Injection Site Reactions

Additional analysis of AEs will be performed for injection site reaction (ISR) related to study drug, which is defined as an AE related to study drug reported as any event within the MedDRA HLT of “Injection Site Reactions”. The following summaries will be provided for each SC injection visit (eg, Day 1, Week 28) and the overall for subjects in Treatment Groups 1 and 2.

- Number of subjects that received SC injection(s)
- Number and percentage of subjects with study drug related ISRs
- Number and percentage of subjects with study drug related ISRs by grade
- Number and percentage of subjects with study drug related ISRs by PT

The denominator for the percentage calculation for the by visit summary and the overall summary will be based on the total number of subjects who receive at least 1 SC injection at the visit of interest and the total number of subjects who receive at least 1 SC injection at any injection visit, respectively.

Duration of the ISR will also be calculated and summarized. Duration of a given ISR event is defined as the ISR stop date minus the ISR onset date plus 1 day. For ISRs with ongoing stop date, stop date will be imputed as last study date or data cut date, whichever is the earliest. Duration of ISR events in days will be summarized using descriptive statistics.

A by-subject listing for study drug-related ISRs and the corresponding duration will be provided.

